	
medication, exclude the case from the calculation for concomitant medication. If the above imputing methods do not help add the date (the first administration date or the final administration date is not provided, etc.), or if the first administration date and the final administration date of concomitant medication are reversed, it should be regarded as a concomitant medication.
 
(‘Clear’ refers to a condition where no ambiguous expressions like “around”, “in the middle”, etc. are included and a number or figure only is provided.)

Concomitant medication: aminosalicylic acid products	See the drug code list and determine from the drug codes.
Concomitant medication: corticosteroid	See the drug code list and determine from the drug codes.
Concomitant medication: immunosuppressant	See the drug code list and determine from the drug codes.
Concomitant medication: antibiotics	See the drug code list and determine from the drug codes.
Concomitant medication: others	Others are the drugs other than aminosalicylic acid products, corticosteroid, immunosuppressant, and antibiotics.
Prior medication: TNF α drug	
When presence/absence treatment history with anti-TNFα drug is “present” in “treatment history with anti-TNFα drug for Crohn’s disease” of the survey form, it should be classified as “with” the history. When the assessment is impossible based on the checkbox, it should be classified as “unknown” whereas no description should be “not provided”. Other cases are “without” the history.

Prior medications	
When a patient had a prior medication of TNFα drug and any of the prior-medication type checkboxes is checked, the patient is regarded as “with prior medications”. When the assessment is impossible based on the checkbox of presence/absence of prior medication/treatment, regard it as “unknown” while no description should be “not provided”. Other cases are “without” prior medications.

Data name	Derivation and calculation methods
Prior medication: aminosalicylic acid products	If aminosalicylic acid drug in the survey form is checked, regard the case as “with aminosalicylic acid drug”. Others are “without aminosalicylic acid drug”.
Prior medication: corticosteroid	If corticosteroids in the survey form is checked, regard the case as “with corticosteroids”. Others are “without corticosteroids”.
Prior medication: immunosuppressant	If immunosuppressant in the survey form is checked, regard the case as “with immunosuppressant”. Others are “without immunosuppressant”.
Prior medication: antibiotics	Otherwise, when antibiotics in the survey form is checked, regard the case as “with antibiotics”. Others are “without antibiotics”.
Prior treatment	When any of the checkboxes of each prior-treatment type in “prior medication/treatment for Crohn's disease is checked in the survey form, regard it as “with prior treatment”. When the assessment is impossible based on the checkbox of presence/absence of prior medication/therapy, regard it as “unknown” while no description should be “not provided”. Other cases are “without” prior treatment.
Prior treatment: surgery	Refer to “[Humira CD Long] Conversion data provided for analysis” to identify it.
Prior treatment: granulocyte and monocyte adsorption apheresis (GCAP)	When GCAP is checked in the survey form, regard it as “with GCAP”. Others are “without GCAP”.
Prior treatment: enteral nutrition therapy	When enteral nutrition therapy is checked in the survey form, regard it as “with enteral nutrition therapy”. Others are “without enteral nutrition therapy”.
Prior treatment: intravenous nutrition therapy	When intravenous nutrition therapy is checked in the survey form, regard it as “with intravenous nutrition therapy”. Others are “without intravenous nutrition therapy”.
Concomitant therapy	It should be described in “non-medicinal treatment/concomitant therapy for Crohn's disease” of the survey form. The data from the first administration date to the final administration date of Humira will be calculated. When concomitant-therapy data are contained under the same rule as the definition of concomitant medications defined in “10.1 General”, regard it “with concomitant therapy”. When “presence/absence of concomitant therapy” in the survey form is not assessable, select “unknown” while it is not provided, select “not provided”. Other cases are “without

Data name	Derivation and calculation methods
	concomitant therapy”.
Concomitant therapy: surgery	Refer to “[Humira CD Long] Conversion data provided for analysis” to identify it.
Concomitant therapy: GCAP	When GCAP is checked in the survey form, regard it as “with GCAP”. Others are “without GCAP”.
Concomitant therapy: enteral nutrition therapy	When enteral nutrition therapy is checked in the survey form, regard it as “with enteral nutrition therapy”. Others are “without enteral nutrition therapy”.
Concomitant therapy: intravenous nutrition therapy	When intravenous nutrition therapy is checked in the survey form, regard it as “with intravenous nutrition therapy”. Others are “without intravenous nutrition therapy”.
Work condition	Just mirror the checked information at “work condition” in the survey form. Of note, if multiple checkboxes are checked or the check is not assessable, regard it as “unknown”. When none of the items are checked, it should be “not provided”.

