10.1. General

Data name	Derivation and calculation methods
Number of sites for this survey	Aggregate the number with DCF code.
The first administration date of Humira	It shall be the oldest date among the dates described in “the administration status of Humira” in the survey form.
The final administration date of Humira	
Do not use for analysis the record of the first administration date of Humira + 1092 days < the first administration date among the data described in “the administration status of Humira” in the survey form.
 
The final administration date of Humira shall be the most recent date among the final administration dates imputed in the following [1] to [4]:
 
[1] Sort data in the order of “the first administration date” of “the administration status of Humira”, dosing frequency and description.
 
[2] If the final date is provided, there is no check on the checkbox of “continued”, and the final administration date can be identified, select the date described as the final administration date.
 
If the final date is not described, the checkbox of “continued” is checked, and the final administration date cannot be identified, follow the below:
 
 • The final record: Impute the first administration date of Humira + 1092 days on the final administration date. • Other than the final record: Impute the first administration date of the next record - 1 day on the final administration date. 
[3] Even though the final dates are described, but the final administration date is incomplete and cannot be identified, follow the below:
 
 • If the year and month are described but the date is unknown, impute the final date of the month as the final administration date. • If the year is described and the month and date are unknown, impute the final date of the year as the final administration date. If the next record has already been generated and the first administration date of the next record comes earlier than the imputed date, impute the first administration date of the next

Data name	Derivation and calculation methods

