	
record - 1 day for the final administration date.
 
Of note, if the final administration date is provided in the record where the final administration date of Humira has been identified according to the above rule and the “continued” checkbox is checked, follow the below:
 
 ● If the described final administration date > the final administration date imputed according to the above rule, select the imputed final administration date as the final administration date of Humira for the patient. ● If the described final administration date <= the final administration date imputed according to the above rule, select the described final administration date as the final administration date of Humira for the patient. 
If the first administration date of Humira + 1092 days < the final administration date of Humira imputed according to the above rule, select the first administration date of Humira + 1092 days as the final administration date of Humira.

Days to the final administration date of Humira	The final administration date of Humira - the first administration date of Humira + 1
Total exposure period (in years)	(Days to the final administration date of Humira + 28) / 364
Discontinued patients	
 • Patients whose final administration date of Humira comes before the first administration date of Humira + 1064 (Week 152) • Patients with a washout period with 60 days or longer. 
*The final administration date of Humira should be the administration date right before the washout of ≥ 60 days starts.

Reason for discontinuation	When a reason for discontinuation is described in the survey form, it is defined as ‘with’ reason for discontinuation. When no such description is found, it is defined as an “unknown/not provided”.
Death cases	At least a piece of data on “death” is found as the outcome of the adverse events during the safety analysis period.
Pediatrics	Patients aged < 15 years
The elderly	Patients aged ≥ 65 years

Data name	Derivation and calculation methods
Presence/absence of complications	When complication data are contained in the survey form, it should be classified as “with complications”. When the description in the survey form is not clear enough (when the check of with/without complications is not assessable or when multiple checkboxes are checked), it should be ‘unknown’ while no description should be ‘not provided’. Other cases are “no complications”.

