	
If all the following [1] to [4] are satisfied, aggregate the data as “160mg \rightarrow 80mg \rightarrow 40mg once every two weeks”. Others are aggregated as “others”.
 
Of note, when data on administration status include only [1], [2] and [3] or when the data ends halfway for some reason, determine whether the case satisfies the criteria from [1] to [4] as of the final data on administration status, and classify it.

Data name	Derivation and calculation methods
Administration status (total number of dosing, total dose)	
 Dosing frequency 
[1] Sort data in the order of “the first administration date” of “the administration status of Humira”, dosing frequency and description.
 
[2] Calculate the dosing interval per data on administration status. “When “once every two weeks” is checked, regard it as a 14-day interval. For others, obtain the frequency from “dosing interval”.
 
[3] Calculate the dosing frequency per data on administration status. Dosing frequency = (the final administration date (the date imputed based on the definition of 10.1 Final administration date of Humira) – the first administration date(after imputed))/dosing frequency (number of days)
 
When the results of [4] and [3] are “>0” (bigger than 0) and “<1” (smaller than 1), count it as 1.
 
If the figure is “>=1” (1 or bigger), round the decimal down to the integer for the dosing frequency.
 
[5] The total number of dosing shall be the total of [4] per patient.
 Dose 
[1] When the dose of Humira is ‘others’, obtain the dose from “Dose_other description”.
 
[2] Calculate the dose per data of the administration status.
 
Dose = the number of dosing * a dose
 
[3] The total dose should be the total of [2] per patient.
 The mean of a dose 
The mean of a dose = the total dose/the total number of dosing

Patients with self-administration	The patients whose registration form has a check on self-administration.
Age	It should be identified based on the date of birth or the first administration date of Humira in the survey form. Of note, if the “date” of birth is incomplete and not provided, impute 1 as the date. When the date of birth is still incomplete even after the above imputation, just mirror the age provided in the survey form.

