12.3. Assessment period for the administration status of Humira

Time allowance of assessment period with the first administration date of Humira as 1 is as follows:

Assessment period	Time Allowance(Day)
the first administration to Week 4 of administration	1-28
after Week 4 of administration to Month 3 of administration	29-84
after Month 3 of administration to Month 6 of administration	85-182
after Month 6 of administration to Year 1 of administration	183-364
after Year 1 of administration to Year 1 and Month 6 of administration	365-546
after Year 1 and Month 6 of administration to Year 2 of administration	547-728
after Year 2 of administration to Year 2 and Month 6 of administration	729-910
after Year 2 and Month 6 of administration to Year 3 of administration	911-1092
Continued as of Year 3 of administration	1093-, patients with 'continued' checked

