12.5. Assessment period for the continued administration of Humira

The assessment period with the first administration date of Humira as 1 is as follows:

Assessment period	Day
At the first administration	1
Week 4 of administration	29
Month 3 of administration	85
Month 6 of administration	183
Year 1 of administration	365
Year 1 and Month 6 of administration	547
Year 2 of administration	729
Year 2 and Month 6 of administration	911
Year 3 of administration	1093

13. Charts to be generated (chart No., chart name)

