Analysis items: number of sites surveyed, number of patients in the safety analysis group, the mean, the maximum, the minimum of the number of patients in the safety analysis group per site

“1.1.3 Progress in survey forms”

Patients for analysis: patients whose survey form was locked

Analysis objective: to show the number of locked cases for each separate volume per patients whose survey form was locked, patients in the safety analysis group, and patients in the effectiveness analysis group.

Analysis items: locked cases in the 1st separate volume, locked cases in the 2nd separate volume, locked cases in the 3rd separate volume, locked cases in the 4th separate volume, locked cases in the 5th separate volume, locked cases in the 6th separate volume

“1.3 A list of the patients excluded from the safety analysis and the patients excluded from the effectiveness analysis (including the reason for exclusion)”

Patients for analysis: patients whose survey form was locked

Analysis objective: to show the list of patients excluded from each analysis group and the reason for exclusion

Analysis item: The reason for exclusion will be displayed for the patients not in the safety or efficacy

analysis.

If more than one reason for exclusion exists in a patient, display them in a comma-delimited manner.

“1.3.1. Excluded patients (aggregation by reason)”

Patients for analysis: registered patients

Analysis objective: to show a list of the reasons for exclusion in each analysis group regarding all the patients in the analysis group.

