Patients for analysis: patients in the safety analysis group, patients in the effectiveness analysis group

Analysis objective: to show the distribution status in the administration period.

Analysis item: Calculate the administration dates based on “days to the final administration date of Humira” of “10.1 General” for the administration period. Then, calculate the number of patients per segment which contains the administration dates in each patient and the percentage to the patients in the analysis group in the Time Allowance defined in “12.3 Assessment period for administration status of Humira”. In addition, calculate summary statistics for the number of days for administration.

“1.6.3 Continuation rate of Humira”

Patients for analysis: patients in the safety analysis group

Analysis objective: to show the continuation rate of Humira using the Kaplan-Meier method.

Analysis items: Calculate At Risk, number of discontinued patients, continuation rate and 95% of continuation rate per assessment period.

Generate the Kaplan-Meier curve with the percentage of the number of discontinued patients to At Risk as the continuation rate.

Note: Follow “12.5 Assessment period for the continuation of Humira administration” for the dates of assessment period.

The days are censored at the first administration date of Humira + 1092 in patients who are still registered at Year 3.

Calculate the analysis items using the Kaplan-Meier method.

At Risk should include the number of patients who are exposed to a discontinuation risk.

“1.7 Administration status of Humira (discontinuation of administration)”

Patients for analysis: patients in the safety analysis group

Analysis objective: to show the number of discontinued patients and the breakdown of the reasons for discontinuation.

Analysis items: Calculate the number of patients in the analysis groups, the percentage to the discontinued patients and patients in the analysis groups, patients ‘with’ reason for discontinuation and unknown/not provided and the percentage to the number of discontinued patients, number of patients per “reason for discontinuation” defined in “11 How to stratify data” and the percentage to the number of discontinued patients.

Note: the reasons for discontinuation may be overlapped in calculation.

In addition, if there are no patients applicable to “multiple choices”, do not display the items of “multiple choices”.

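### SAP 10.1 treats an open last dosing record as running to first dose + 1092 days, with no visible check against the last collected CRF volume: a minor overstatement of exposure in an unknown, possibly zero, number of patients

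*SAP*

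**What the plan says.** SAP 10.1 builds the final administration date from the dosing records. When the last record has no final date, is ticked as continued and cannot be dated otherwise, the rule is "The final record: Impute the first administration date of Humira + 1092 days on the final administration date". Three provisions limit it:

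- If the form holds both a date and the tick, and the written date is not later than the imputed one, the instruction is to "select the described final administration date as the final administration date of Humira for the patient".
- No final date may lie beyond + 1092.
- A washout of 60 days or more moves the date back to the last dose before the gap.

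The date then feeds these outputs:

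- **1.6.1:** the number of doses is computed from "the date imputed based on the definition of 10.1 Final administration date of Humira", and total dose follows from it.
- **1.6.2:** the table is to "calculate the number of patients per segment which contains the administration dates in each patient". In SAP 12.3 the class from Day 1093 is "Continued as of Year 3 of administration".
- **1.7:** a patient is discontinued if the final date is before + 1064 or there is such a washout.
- **2.6 and 2.7:** discontinued patients are counted to final date + 28 days, all others to first dose + 1120 days.
- **2.4.2:** events count up to final date + 28 days. The denominator of the rate is not named. SAP 10.1 separately defines a Total exposure period, (days to final date + 28)/364.
- **1.6.3:** Kaplan-Meier times are censored at + 1092 for patients still registered at Year 3.

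Protocol 6(3) plans six half-yearly CRFs per patient. Protocol 8(1) handles patients lost through transfer or other reasons as discontinued from the survey.

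**The concern.** A continued tick with no date means one thing when all six volumes are in, and another when the last volume is the second. In the first case + 1092 is a fair reading. In the second, nothing is known after about one year, yet the rule supplies two more years of treatment.

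The three limiting provisions do not reach this patient. There is no written date, the cap does not shorten a value already at + 1092, and no dosing gap is recorded. The protocol would call the patient a survey discontinuation, while the SAP would call the same patient treated to Year 3.

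The error runs one way. Exposure and persistence look longer, and late-period incidences look lower. Under one reading of 2.4.2, so do the rates for malignancy and serious infection, which are the stated focus of the survey.

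**Working it through.** **The plan's own day counts.** 6 × 182 = 1092, which is Day 1093 when the first dose is Day 1, as in SAP 12.5. Week 152 is 152 × 7 = 1064 and Week 160 is 160 × 7 = 1120. The plan states no exposure figure that could be reproduced.

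**Per patient.** Days to the final date = final − first + 1; exposure days add 28; years divide by 364. Under the rule the result is 1092 + 1 + 28 = 1121 days (3.08 years), whatever the last volume. If documentation ends with volume v, it is 182v + 1 + 28:

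| Last volume v | Last documented day | Exposure days | Years | Excess credited (days) |
|---|---|---|---|---|
| 1 | 183 | 211 | 0.58 | 910 |
| 2 | 365 | 393 | 1.08 | 728 |
| 3 | 547 | 575 | 1.58 | 546 |
| 4 | 729 | 757 | 2.08 | 364 |
| 5 | 911 | 939 | 2.58 | 182 |
| 6 | 1093 | 1121 | 3.08 | 0 |

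**1.6.1.** A two-weekly record open from first dose + 42 days is credited with (1092 − 42)/14 = 75 doses. If last documented at Day 183, it should be (182 − 42)/14 = 10.

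**1.6.2 and 1.7.** Days to the final date are 1093, the first day of the Year 3 class. Since 1092 is later than 1064, the patient is not discontinued.

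**2.6 and 2.7, Day 911-1092.** Assume 500 patients, k affected with losses spread evenly over volumes 1 to 5, and all others followed to the end. Volumes 1 to 4 end, with 28 days added, by Day 757, so 4/5 of the k are wrongly in the denominator. For k = 5, 25 and 50 that is 4, 20 and 40 of 500, diluting the incidence by 0.8%, 4.0% and 8.0%.

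**2.4.2, only if the denominator is the Total exposure period.** With 500 patients, k affected with true exposure t days, and O days for each of the others:

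understatement = k(1121 − t) / [(500 − k)·O + k·1121]

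With O = 1121 the denominator is 560,500 days (1539.8 patient-years):

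| Affected | All lost at Day 911 | Evenly spread (mean t = 575) | All lost at Day 183 |
|---|---|---|---|
| 5 (1%) | 0.2% | 0.5% | 0.8% |
| 25 (5%) | 0.8% | 2.4% | 4.1% |
| 50 (10%) | 1.6% | 4.9% | 8.1% |

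For example, 25 × 910/560,500 = 4.1%. If the others average 2 years (O = 728 + 28 = 756), the denominator for k = 25 is 475 × 756 + 25 × 1121 = 387,125, and the understatement is 1.2%, 3.5% and 5.9%.

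**Scale.** SAP 4.3 takes about 1.0% malignancy, so about 5 cases in 500. 5/1539.8 = 0.325 per 100 patient-years, with exact Poisson 95% limits 1.62/1539.8 and 11.67/1539.8, that is 0.105 to 0.758. With 25 patients lost at Day 183, true person-time is 537,750/364 = 1477.3 years and the rate is 0.338.

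**1.6.3, only if these patients are carried to + 1092.** Assume 100 true stops in 500, half before Day 547 and half after. Carried forward, continuation is 400/500 = 80.0%. With 25 censored at Day 547 it is 450/500 × 375/425 = 79.4%. With 50 censored it is 450/500 × 350/400 = 78.8%.

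**The case against.** The strongest reply is that few such records may exist.

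- Protocol 6(3) requires a CRF without delay when Humira is stopped, and allows reinvestigation of forms.
- Protocol 8(3) collects the reasons for ending the investigation, including no visits.
- Only locked forms enter the safety group. Table 1.3.1 lists safety not assessable and unconfirmed data credibility among the exclusion reasons.
- SAP 10.1 announces four imputation steps but numbers only three in the visible text. The CRF layout and the inclusion/exclusion document are not shown. A check could sit in any of these.

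All of this narrows the group, possibly to zero. It does not remove the case of a patient transferred while on drug, because the prompt CRF is tied to stopping treatment.

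A reader might also infer more than the documents support:

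- *That the problem would stay hidden.* No dedicated count is planned, but 1.1.3 counts "locked cases in the 1st separate volume, locked cases in the 2nd separate volume" and so on to the sixth, separately for the safety group. Patients in the Day 911-1092 and Year 3 classes of 1.6.2 should generally have a volume 6. A clear excess over the locked sixth volumes would approximate the affected number. Listing 1.4 also shows each final date.
- *That the malignancy and infection rates are certainly understated.* 2.4.2 names no denominator. The shared 28 days make the Total exposure period likely, but not stated.
- *That the continuation curve is certainly too high.* 1.6.3 limits censoring at + 1092 to patients still registered at Year 3, and does not say how a patient who left earlier is handled.
- *That the protocol's expected substantial attrition measures the problem.* That phrase in Protocol 2 combines stopping and withdrawal, and says nothing about undated open records.

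**Conclusion.** The concern holds as a minor point. As visible, the rule gives a wrong final date for a patient whose survey ended before Year 3 on drug with an undated open record. The effects on 1.6.1, 1.6.2, 1.7 and 2.6/2.7 follow directly from the SAP text. Those on 2.4.2 and 1.6.3 are conditional.

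The rule is sound for patients documented to Year 3. Patient-count incidences (2.4.1.1, 2.4.1.2, 2.17.1) are unaffected.

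The percentages above rest on assumed numbers and timing of losses. At 5% affected with the others treated 3 years, the 2.4.2 understatement of 0.8 to 4.1% is small beside the sampling uncertainty of about five malignancies.

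**What to change.** In SAP 10.1, apply + 1092 to an open, undated last record only when volume 6 is locked. Otherwise set the final date to first dose + 182 × v days, where v is the last locked volume, and never before the start of that record. Volumes 1 to 5 then give Days 183, 365, 547, 729 and 911, which are the days in SAP 12.5. Volume-6 patients are unchanged.

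Then:

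- Censor these patients at that date in 1.6.3.
- Show them in 1.6.2 and 1.7 as follow-up ended on treatment. This must be written down, because the + 1064 rule would otherwise class them as discontinued.
- End their at-risk time in 2.6/2.7 and their person-time in 2.4.2 at that date + 28 days.
- Name the 2.4.2 denominator and show 2.4.2 under both rules.
- Report the number imputed to + 1092 by last locked volume. If every one has volume 6, that line settles the matter.
- List separately any later event that arrives through the AE matching list.

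The cost is SAP wording and one reprogrammed derivation, since locked volumes are already needed for 1.1.3. There are three downsides. Person-years fall slightly. A last volume closed early may still be over-credited by less than 182 days. A few late events may fall outside the 2.4.2 window: losing one of five malignancies would move 0.325 to 4/1539.8 = 0.260 per 100 patient-years, a 20% change. That is why the separate list and both rules are needed.

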- 2) Physicians who have experienced anti-TNF α antibody treatment to patients with Crohn's disease ^{*2}

^{*1} This condition will be used during the all-case investigation of Humira in Crohn's disease

^{*2} This requirement will be used after the conditions for approval were completely removed.

6. Methods of the investigation

(1) Principles of the investigation

Patients who receive Humira in the applicable institutions (that satisfy the criteria for institutions and physicians and have concluded agreements with AbbVie GK.) will be registered using a central registration method.

(2) Procedures for requesting cooperation and concluding agreements

- 1) Medical representatives will provide investigators and other healthcare professionals with a complete set of informational materials on safety measures (for physicians expect the investigators participating in the all-case investigation), and will inform them about the characteristics of Humira, the purpose of the investigation, patients to be investigated, and methods of investigation.

(3) Procedures of the investigation

- 1) A paper-based case report form (CRF) will be used to collect investigation data.
- 2) Each patient will be observed during 3 years after the onset of Humira treatment.
- 3) When the treatment with Humira is selected for a patient who has expressed his/her consent for treatment, the investigator will fill out a registration form without delay* and submit it to the registration center to register the patient.
- * Basically, we accept registration forms with a postmark date within 14 days after the date of first administration of Humira (the first treatment date is Day 0).
- 4) Investigators will fill out the CRF for each patient every 6 months for 3 years after the initiation of Humira treatment, and provide it to a medical representative (MR). Accordingly, a total of 6 copies of CRFs will be obtained for each patient. When a patient discontinues Humira treatment during the investigation period, the investigator will fill out the CRF for the patient without delay at the time of discontinuation of treatment, and provide it to a MR.
- 5) The sponsor (AbbVie GK.) will confirm the contents of the registration form and CRFs, and perform reinvestigation whenever necessary.

(4) Adverse Event Reporting

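### Incomplete last-dose dates are set to the end of the month or year, which lengthens exposure for patients who stopped and can class some of them as not discontinued

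*SAP*

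**What the plan says.** SAP section 10.1, under the final administration date of Humira, handles incomplete end dates in step [3]. The step applies where "Even though the final dates are described, but the final administration date is incomplete and cannot be identified". It has two rules:

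- Day unknown: "If the year and month are described but the date is unknown, impute the final date of the month as the final administration date".
- Month and day unknown: "impute the final date of the year as the final administration date".

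Two limits follow. The day before the next record's start is used "If the next record has already been generated and the first administration date of the next record comes earlier than the imputed date". Any final date later than first dose + 1092 days is cut back to that day.

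The general date table in SAP 9.1 would treat an unknown month and day as null. Section 9.1 defers to Chapter 10, however, so step [3] governs.

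The same section defines a discontinued patient by a final date earlier than first dose + 1064 days (Week 152), or by a washout of at least 60 days. A recorded reason for discontinuation is not part of the definition. Total exposure in years is (days to final date + 28)/364.

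Chart 1.6.3 (SAP 13.1) gives a Kaplan-Meier continuation rate, with patients still registered at Year 3 "censored at the first administration date of Humira + 1092". Protocol section 6(3), item 4, has forms completed every six months, and when treatment stops the investigator is to "fill out the CRF for the patient without delay at the time of discontinuation of treatment". SAP chart 1.1.3 counts six separate survey volumes.

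**The concern.** Step [3] takes the latest day that the entry allows. A patient's last record has no next record, so only the three-year cap restrains it. That cap lies 28 days after the Week 152 threshold, so it cannot keep a stopper on the discontinued side. The 60-day washout criterion does not help either, because imputed dosing runs without a break to the imputed date.

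The final date feeds several outputs:

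- the discontinued flag, the continuation curve (1.6.3) and the table of reasons (1.7), from which a reclassified stopper disappears;
- number of doses and total dose;
- patient-years and the event window in chart 2.4.2, which reports the priority items (malignant tumour, serious infection);
- the at-risk periods in charts 2.6 and 2.7.

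The six-month volume that holds the record gives a tighter bound, and the rule does not use it.

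**Working it through.** The plan states no figure for the effect of this rule, so there is none to reproduce.

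**Mechanism.** Let F be the first dose. With only the year known, the imputed date is min(31 December of the recorded year, F + 1092). The patient is classed as not discontinued when this date is at or after F + 1064. For a stop before F + 1064, that happens when F + 1064 falls on or before 31 December of the recorded year.

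**Worked dates, year only recorded.**

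| First dose | True stop | F + 1064 | Imputed | Gain | Status |
|---|---|---|---|---|---|
| 1 Dec 2011 | 15 Jan 2014 (day 777) | 30 Oct 2014 | 27 Nov 2014 (cap) | 316 days | not discontinued |
| 2 Jul 2012 | 15 Jan 2015 (day 928) | 1 Jun 2015 | 29 Jun 2015 (cap) | 165 days | not discontinued |
| 2 Jul 2012 | 15 Mar 2014 (day 622) | 1 Jun 2015 | 31 Dec 2014 | 291 days | discontinued |

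In the first row, exposure rises from (777 + 28)/364 = 2.21 years to (1093 + 28)/364 = 3.08 years, which is a completer's value.

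**Average effect per record.** Simulation of 400,000 stoppers. First doses are uniform over the registration period (November 2011 to October 2013, Protocol section 7). Stop times are assumed in two ways: uniform over days 0 to 1063, or front-loaded (exponential with mean 400 days, truncated at 1064).

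| | Uniform stops | Front-loaded stops |
|---|---|---|
| Year only: mean gain | 166 days (maximum 365) | 178 days |
| Year only: reclassified | 17% | 5% |
| Day unknown: mean gain | 15 days (maximum 30) | 15 days |
| Day unknown: reclassified | 1.4% | 0.3% |

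With exponential stopping scaled to 30% or 50% of patients stopping by three years, the year-only results are 168 to 170 days and 13 to 15%, within the same range.

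**Midpoint rule for comparison.** For year-only records, take the midpoint of the interval bounded by the recorded year, the 182-day survey volume and the cap. The mean error is then about 1 to 6 days, and 0.1% or fewer are reclassified.

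**Aggregate (assumed).** Take 500 patients, of whom 200 stop, and suppose that 2 to 10% of stoppers (4 to 20 patients) have a year-only last date.

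- Total exposure, uniform stops (mean stop day 531): 300 × 1121/364 + 200 × (531 + 29)/364 = 924 + 308 = 1,232 patient-years.
- Excess, uniform stops: 4 × 166/364 = 1.8 to 20 × 166/364 = 9.1 patient-years, or 0.15 to 0.74%.
- Total exposure, front-loaded stops (mean about 320 days): 924 + 200 × (320 + 29)/364 = about 1,116 patient-years.
- Excess, front-loaded stops: 4 × 178/364 = 2.0 to 20 × 178/364 = 9.8 patient-years, or 0.18 to 0.88%.
- Reclassified: at most 20 × 17.2% = 3.4 patients; with front-loaded stops, 20 × 4.7% = 0.9.

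**The case against.** **Not every step [3] record is a known stop.** This stands. Administration records also hold dose and interval changes, where the next-record limit applies, and an incomplete last date can belong to a patient who reached Year 3. The per-record figures apply only to patients who stopped and whose last record is incomplete.

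**Rates need not fall.** A reader might infer that malignancy and serious-infection rates per 100 patient-years are necessarily understated. The documents do not support that. Chart 2.4.2 counts events up to the final date + 28, so a later date lengthens the event window too, and SAP 10.2 admits events from outside the survey form. Because the protocol ends the survey at discontinuation, the denominator probably grows more than the numerator. That makes lower rates likely, not certain.

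**The Kaplan-Meier effect is not fully specified.** Censoring at + 1092 is for patients still registered at Year 3, and the SAP does not settle whether a documented stopper would count as such. On either reading the patient stays at risk until the imputed date, so continuation before then is too high.

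**It is a common convention and the effect is small.** The SAP uses the same latest-date rule for concomitant-medication end dates. Six-monthly forms and sponsor reinvestigation should keep year-only dates few. As an illustration, 5 malignancies in 1,200 patient-years is 0.42 per 100 (exact 95% CI 0.14 to 0.97), and a 0.8% change in exposure moves it by about 0.003. This limits the importance. It does not remove the one-sided error in dates, exposure and continuation.

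**Some possible bounds may not be held.** Neither a form completion date nor a date of death is listed among the CRF items in Protocol section 8(3), so a fix should not depend on them. The six-month volume is supported by both documents.

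**Conclusion.** The point holds as a minor one. For stoppers with an incomplete last date, the rule can push exposure, dose counts and continuation only upward. A year-only date adds about 166 to 178 days on average and turns about 5 to 17% of such stoppers into not discontinued. An unknown day adds about 15 days and reclassifies about 0.3 to 1.4%. These figures rest on assumed stop times and uniform enrolment.

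The documents do not say how many final dates are incomplete, so the total effect is unknown. With an assumed 2 to 10% of 200 stoppers it is about 2 to 9 patient-years (9.8 if stops come early), under 1% of exposure, and at most about 3 patients. A reader might infer that the survey's safety conclusions are materially distorted, or that 17% of all stoppers are lost from the discontinued group. Neither follows, because the percentages apply only to stoppers with a year-only last record.

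**What to change.** Amend SAP 10.1 step [3] as follows:

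1. For a last record not ticked as continued, impute the midpoint between the earliest and latest dates that the record allows. The bounds are the recorded month or year, the six-month volume that holds the record, any next record's start − 1 day, and first dose + 1092. Add a form completion date or a death outcome date as a bound only if it is in the database.
2. Where the form records a discontinuation, and the recorded period and volume allow a stop before first dose + 1064, do not let the imputed date alone class the patient as not discontinued. Leave the Week 152 definition unchanged for complete dates. An unconditional override would treat a late stop with an unknown day differently from the same stop with a full date.
3. Report how many final dates were imputed, separately for unknown day and unknown month.

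The cost is a few lines of SAP text and programming. The result will be slightly shorter exposure and slightly less favourable continuation.
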